### **6. Statistical Considerations**

- **Software:** SPSS v25.0; MATLAB for data organization/graphs.
- **Normality:** Shapiro-Wilk test.
- **Reliability:** Intraclass correlation coefficient (ICC) and coefficient of variability (CV).
- **Primary Analysis:** Two-way repeated measures ANOVA (Condition × Time).
- **Post Hoc:** Bonferroni correction.
- **Effect Sizes:** Cohen's d and partial eta squared ( $\eta^2$ ).
- **Significance Threshold:**  $p < 0.05$ .

---

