## **2. Objectives**

### **Primary Objective:**

- To determine the acute effects of tissue flossing versus foam rolling on AROM, viscoelastic muscle properties, and jump performance.

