### **Secondary Objectives:**

- To compare the magnitude and time course of TF- and FR-induced changes at 1 and 15 minutes post-intervention.
- To explore whether TF provides superior improvements in force development compared with FR and CON.

---

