### 3. Study Design

- **Design:** Randomized, controlled, crossover study.
- **Conditions:**
  1. Tissue Flossing (TF)
  2. Foam Rolling (FR)
  3. Control (CON)
- **Population:** 30 male adolescent handball players.
- **Randomization:** Intervention order randomized using [www.randomizer.org](http://www.randomizer.org).
- **Washout:** Minimum 24 h, maximum 5 days between sessions.
- **Blinding:** Due to the nature of interventions, blinding participants was not feasible; however, outcome assessors were blinded to condition.

---

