#### Sample Size Justification:

Power analysis (G\*Power 3.1.9.4) indicated  $n = 21$  required (effect size = 0.398,  $\alpha = 0.05$ , power = 0.8). To account for dropout, 30 participants enrolled.

---

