### **Outcome Measures:**

1. **Active Range of Motion (AROM):** Active Knee Extension (AKE) test.
2. **Viscoelastic Muscle Properties:** Stiffness and tone measured with MyotonPRO in VL, RF, and BF.
3. **Jump Performance:** CMJ height and braking rate of force development via force plate.

**Timing of Assessments:** Baseline, 1 min post, 15 min post intervention.

---

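### Efficiency, not validity: as naturally read, the primary ANOVA treats each session's baseline as a level of Time, so the TF-versus-FR contrast gains nothing from adjusting for it

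*Protocol*

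**What the plan says.** Protocol Section 6 (Statistical Considerations) gives the primary analysis as "Two-way repeated measures ANOVA (Condition × Time"), followed by post hoc tests with "Bonferroni correction". It names no covariate and does not list the levels of Time.

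Section 5 (Outcome Measures) gives the assessment times as "Baseline, 1 min post, 15 min post intervention". Nothing else in the protocol defines Time, so the natural reading is three levels, of which baseline is the first.

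Section 3 describes a "Randomized, controlled, crossover study" with three conditions (TF, FR and control, CON), and a washout of "Minimum 24 h, maximum 5 days between sessions". Each condition therefore has its own session and its own baseline.

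The comparison of interest is TF with FR. The primary objective is "To determine the acute effects of tissue flossing versus foam rolling on AROM, viscoelastic muscle properties, and jump performance", and a secondary objective is "To compare the magnitude and time course of TF- and FR-induced changes at 1 and 15 minutes post-intervention".

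**The concern.** Under this model the TF-versus-FR comparison at a post time can be made in two ways:

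- **Through the Condition × Time interaction.** This compares changes from baseline. It fixes the baseline slope at 1 and carries all of the noise in the baseline measurement.
- **Through a post hoc comparison of conditions at 1 or 15 minutes.** This uses the post value alone. It fixes the slope at 0 and discards what the baseline says about the participant's state that day.

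A covariate for the session baseline lets the data choose the slope. Sessions are one to five days apart, so the participant's state can differ between them, and the trial already measures it. What is at stake is the precision of the TF–FR estimates with at most 30 participants. The planned ANOVA is not biased and does not inflate the type I error.

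**Working it through.** **Inputs from the protocol.** Three conditions in separate sessions (Section 3); three assessments per session (Section 5); 21 participants required and 30 enrolled (Section 4); Condition and Time as the only factors (Section 6).

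**The plan's own figure.** The sample size rests on "effect size = 0.398", alpha 0.05 and power 0.8. The effect-size metric and the test are not stated. Taking the effect as Cohen's f and testing a Condition × Time interaction with df1 = 4, df2 = 4(N − 1) and noncentrality f² × 4(N − 1), N = 21 gives 0.398² × 80 = 12.67 and power 0.8004. So n = 21 is reproduced under one plausible set-up. Other settings also come close, so this does not show which was used, and the point below does not depend on it.

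**Assumed quantity.** The correlation r is not in the protocol, so a range from 0 to 0.9 is shown. It applies after stable differences between participants are removed, which the crossover already does, so it may be lower than a raw baseline–post correlation.

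**Formulas** for the TF–FR contrast at one post time. var_s is the session-to-session variance within a participant, var_e the variance of a single measurement about it (equal at baseline and post), and r = var_s/(var_s + var_e):

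- change score: 4 var_e / n
- post value alone: 2(var_s + var_e) / n
- baseline-adjusted: 2(var_s + var_e)(1 − r²) / n

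Since var_e = (1 − r)(var_s + var_e), the ratio adjusted/change is (1 − r²)/[2(1 − r)] = (1 + r)/2. The ratio adjusted/post-only is 1 − r². In large samples neither exceeds 1.

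**Small-sample check.** Estimating a slope and period effects costs something at these sample sizes. The simulation used 6,000 runs per cell, three periods, each participant's order drawn from the six sequences, no true period effect and participant effects removed. The adjusted model has condition, period and session baseline; the comparators have condition only. Variance ratios:

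| r | adj/change, theory | adj/change, n = 30 | adj/change, n = 21 | adj/post, theory | adj/post, n = 30 |
|---|---|---|---|---|---|
| 0 | 0.50 | 0.52 | 0.54 | 1.00 | 1.05 |
| 0.3 | 0.65 | 0.67 | 0.69 | 0.91 | 0.94 |
| 0.5 | 0.75 | 0.80 | 0.81 | 0.75 | 0.77 |
| 0.7 | 0.85 | 0.90 | 0.91 | 0.51 | 0.52 |
| 0.8 | 0.90 | 0.94 | 0.98 | 0.36 | 0.37 |
| 0.9 | 0.95 | 1.00 | 1.02 | 0.19 | 0.20 |

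With period also in the change-score model, the n = 30 ratios are 0.50, 0.65, 0.78, 0.87, 0.91 and 0.96.

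**In participants.** At r = 0.5 and n = 30, 30 × 0.80 = 24. Two repeat simulations gave 0.81 and 0.76 for this cell, that is 24.3 and 22.8 participants.

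**Worst losses.** Across the simulations, adjustment loses about 4 to 6% against post values alone at r = 0 with n = 30, and about 8 to 9% with n = 21. At r = 0.9 it loses at most about 3% against change scores.

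**The case against.** The strongest reply is that nothing here is wrong. The ANOVA is valid and conventional, and it speaks directly to an objective framed as change over time. Section 6 is a short outline, and an analysis plan not shown could name the contrasts or add a covariate.

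The size can also be put less favourably. Against the better of the two comparators at each r, the n = 30 ratios are 1.05, 0.94, 0.80, 0.90, 0.94 and 1.00, so only two of the six values of r show a variance gain of 10% or more. The 24-participant example sits at r = 0.5, where the two comparators are equal and the gain over the better one is largest. Even there the interval narrows by only about 11% (√0.80 = 0.89), and at r = 0.7 by about 5% (√0.90 = 0.95). The simulation covers one post time, whereas the proposed model has two.

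Part of this stands. The gain is modest against the better comparator, r is unknown, and the concern depends on the natural reading of Time. It does not remove the point:

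- The protocol does not leave the primary model open; it names one without a covariate.
- The better comparator cannot be chosen in advance without knowing r. Adjustment comes close to or beats the better one throughout, with small worst-case losses.
- A further check with one baseline slope shared by both post times kept the gain.
- Change from baseline within each condition can still be reported descriptively, so the time-course objective is still served.

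**Conclusion.** The concern holds as a matter of efficiency only. On the natural reading, the named primary analysis uses the session baseline with a slope fixed at 1 or not at all, and adjustment is more precise than both over most of the range examined. At n = 30 the variance reduction against change scores is about 33% at r = 0.3, 20% at r = 0.5, 10% at r = 0.7 and nil at r = 0.9. Against post values alone it is about 6%, 23%, 48% and 80% at the same values.

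This rests on an assumed range for r, equal variances at baseline and post, and baseline being a level of Time. It is a worthwhile improvement at little cost, not a defect that threatens the trial's conclusions. Confidence is medium because r is unknown.

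**What to change.** In Section 6, make the primary analysis a linear mixed model on the 1-minute and 15-minute values:

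- **Fixed effects:** condition, time, condition × time, period, and session baseline entered as the participant's mean baseline plus the session's deviation from it. The split keeps between-participant baseline differences out of the treatment contrast.
- **Random effects:** participant, and session within participant.
- **Report:** TF–FR, TF–CON and FR–CON at each post time with confidence intervals and the Bonferroni correction already planned, and within-condition change from baseline descriptively.

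As a side benefit, the model can use every available session if a participant misses one, which is valid if data are missing at random.

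The cost is a short rewording of the analysis section and no new data. Statistically it is one within-participant slope and two period effects, already counted in the simulated ratios. Partial eta squared does not carry over directly, so the effect-size line needs a matching edit. Section 9 requires Ethics Committee approval of any amendment. The change should be fixed before results by condition are examined; after that, the adjusted model is better presented as a supporting analysis.

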#### Exclusion Criteria:

- Prior experience with TF.
- Regular use of FR.
- Contraindications to compression therapy or vigorous exercise.

**Recruitment:** Participants recruited from handball training centers in Prague.

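### The primary model omits period although session order is randomised: no bias, but any drift across sessions costs precision or makes the tests conservative

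*Protocol*

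**What the plan says.** Protocol Section 3 describes a "Randomized, controlled, crossover study" of tissue flossing (TF), foam rolling (FR) and control in 30 players. On allocation it says "Intervention order randomized using" a website. It does not say whether the six possible orders are balanced. The spacing is "Minimum 24 h, maximum 5 days between sessions".

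Section 5 sets the assessments in every session at "Baseline, 1 min post, 15 min post intervention". Section 6 then names the primary analysis, "Two-way repeated measures ANOVA (Condition × Time", with "Bonferroni correction" for the post hoc tests. Time therefore means the three assessments within a session. Neither Section 6 nor any other part of the protocol brings period, session number or order into the analysis.

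Among the secondary objectives in Section 2 is "To compare the magnitude and time course of TF- and FR-induced changes at 1 and 15 minutes post-intervention". The term that answers it is Condition × Time.

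**The concern.** In a crossover, each player's condition differences are also differences between sessions. If players do better or worse from session 1 to session 3 whatever the condition, a model without period leaves that drift either in the condition estimates (when orders are unequal by chance) or in the error term.

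Which results are exposed depends on the kind of drift:

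- **Constant shift of a whole session.** It cancels from the change from baseline, and so from Condition × Time. It stays in the Condition main effect and in comparisons of conditions at a single time point. Section 6 does not exclude either of these.
- **Shift in the within-session change.** The response itself grows or fades with session number. This stays in Condition × Time, and a Period main effect alone would not remove it; Period × Time is needed.

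Drift is plausible, since the same jump and knee-extension tests are repeated three times within days and no familiarisation session is described. That is an inference; the protocol reports no drift. At stake are precision and power, not validity.

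**Working it through.** **Inputs.** From the protocol: n = 30, three conditions, three time points per session, randomised order. Assumed, because the protocol gives none: SD 1 for a single measurement within a player; within-session correlation r = 0.5 (0.3 and 0.7 as alternatives); linear drift b = 0.125, 0.25 or 0.5 SD per session. The protocol's only design figure, n = 21 from the power analysis, neither enters this point nor changes because of it.

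**1. Unrestricted orders: variance of the TF minus FR contrast.** The two session numbers differ by ±1 in 4 of the 6 orders and by ±2 in the other 2. The mean square is (4×1 + 2×4)/6 = 2.

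- One time point: per-player variance 2 + 2b², ratio 1 + b².
- Change from baseline, constant shift: nothing is added.
- Change from baseline, drift in the change: 4(1−r) + 2b², ratio 1 + b²/[2(1−r)].
- Condition main effect, constant shift: the session mean has variance (1 + 2r)/3 = 0.667 at r = 0.5, ratio 1 + 1.5b².

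| Variance increase | b = 0.125 | b = 0.25 | b = 0.5 |
|---|---|---|---|
| One time point | 1.6% | 6.3% | 25% |
| Condition main effect, r = 0.5 | 2.3% | 9.4% | 37.5% |
| Change, drift in the change, r = 0.3 | 1.1% | 4.5% | 18% |
| Same, r = 0.5 | 1.6% | 6.3% | 25% |
| Same, r = 0.7 | 2.6% | 10% | 42% |

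For one time point the standard error rises by 0.8%, 3.1% and 11.8% (square roots of 1.016, 1.063 and 1.25).

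**2. Net of the cost of the period terms.** Under unrestricted orders, fitting the period terms itself costs about 3% in variance. Simulation (4,000 trials per setting, r = 0.5, Monte Carlo error about 2%) gives n × variance without and with them:

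| | b = 0 | b = 0.125 | b = 0.25 | b = 0.5 |
|---|---|---|---|---|
| One time point, constant shift | 1.99 / 2.08 | 2.04 / 2.07 | 2.19 / 2.11 | 2.47 / 2.01 |
| Change, drift in the change | – | 2.06 / 2.11 | 2.14 / 2.04 | 2.40 / 2.02 |

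The formula gives a net gain of 1 − 1.03/1.25 = 18% at b = 0.5 and 1 − 1.03/1.063 = 3% at 0.25. At 0.125 there is none (1.03 against 1.016). The simulated gains at 0.5 are 1 − 2.01/2.47 = 19% and 1 − 2.02/2.40 = 16%. Type I error without or with the period terms was 4.5 to 5.7% throughout.

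**3. Balanced orders: level of the tests.** The drift cancels from the condition means but stays in the error term.

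- *Condition test, constant shift.* Each player's drift sum of squares is 2b², so the expected error mean square is 0.667 + 60b²/58. At b = 0.5 that is 0.925, a ratio of 1.388. The critical value 3.156 then acts like 3.156 × 1.388 = 4.38. The tail of F(2, 58) there is (1 + 8.76/58)^(−29) = 1.7%. For b = 0.125 and 0.25 the same steps give 4.7% and 3.8%. Simulation: 4.5%, 3.6%, 1.3% without period; 4.8%, 4.5%, 4.9% with it.
- *Condition × Time, drift in both post-intervention values.* The drift adds 2b² × 2/3 per player, or 40b²/116 to an error mean square of 0.5. At b = 0.5 the ratio is 1.172, the effective critical value 2.450 × 1.172 = 2.87, and the tail of F(4, 116) about 2.6%. Simulation: 4.8%, 4.7%, 2.3% without Period × Time; 4.9%, 5.4%, 4.9% with it.

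**4. Power, under other assumptions.** A separate simulation (2,000 trials per setting) used independent residuals of SD 1 and a 0.6 SD post-intervention effect. A constant shift of 0.5 SD per session left the Condition test with power 0.53 instead of 0.76 under simple randomisation, and 0.47 instead of 0.78 under balanced orders. With r = 0 the session mean is less variable, so the same drift weighs more. Interaction power was not affected by a constant shift (0.35 to 0.38). With a shift of 1 SD per session in the post-baseline values, it fell from 0.36 to 0.27 (simple) or 0.20 (balanced).

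**The case against.** The strongest reply is that nothing here is invalid. Order is randomised, so a within-player ANOVA is unbiased and its type I error is at or below 5%; period terms only improve efficiency. The interaction carries the objective on induced changes, and a constant shift drops out of it exactly. To harm that term, the response itself must vary with session number. The protocol gives no evidence of this, and the warm-up is the same in all sessions. At 0.125 SD the net gain is nil, at 0.25 SD only a few per cent, and with no drift and unequal orders the period terms lose about 3%. The allocation method is not stated, so the variance inflation may not arise at all. A SAP might also add period.

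Most of this stands, and it limits the point to one of precision and power. It is also true that excluding players with "Prior experience with TF" does not support drift: each player meets flossing once, so its novelty belongs to that condition wherever it falls. Two parts do not stand. The protocol does not leave the model open; it names the primary analysis and both its factors, so a SAP adding period would change a stated analysis. Balanced orders do not settle the matter either, because the drift then inflates the error term and the tests become conservative.

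**Conclusion.** The concern holds. The primary model ignores a design factor that the randomisation creates. The consequence is lost precision and a chance shift in the estimates if orders are unrestricted, or conservative tests if they are balanced. There is no systematic bias and no excess of false positives.

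The size rests wholly on an assumed drift. It is negligible at 0.125 SD per session and modest at 0.25 SD. At 0.5 SD it is material: 25% more variance for a contrast at one time point, or a nominal 5% Condition test run at between 1 and 2%. Condition × Time is affected only by drift in the within-session change; at 0.5 SD with balanced orders its level is then between 2 and 3%. The model should be changed because the remedy is cheap, but the omission does not invalidate the trial. Confidence is medium, since neither the drift nor the allocation method is documented.

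**What to change.** In Section 6, replace the two-way ANOVA with a mixed model containing Condition, Time, Condition × Time, Period and Period × Time. Take Period from the recorded session order, with player and session within player as random effects. Add player by Time as a random effect if the error strata of the ANOVA are to be kept; the degrees of freedom below assume that. Base the Bonferroni-corrected comparisons on this model.

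In Section 3, state how the orders are allocated. If allocation is still open, assign the six orders to five players each; this removes the variance cost of the period terms.

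The cost is 2 error degrees of freedom at session level (29 × 2 = 58 down to 56; critical F 3.156 to 3.162) and 4 for the interaction (29 × 2 × 2 = 116 down to 112; critical F 2.450 to 2.453). If there is no drift and orders are unbalanced, variance rises by about 3%. No extra players or visits are needed, and the model can be fitted after data collection as long as session order was recorded.

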### **7. Ethics and Safety**

- Conducted in line with Declaration of Helsinki.
- Written informed consent obtained from all participants (and guardians, if  $<18$ ).
- Right to withdraw at any time without consequence.
- Minimal risk: interventions are widely used in sports training.

---

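### The primary repeated measures ANOVA drops any player with an incomplete set of nine measurements, so completed TF and FR sessions can be lost from the main contrast in a trial that allows for dropout

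*Protocol*

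**What the plan says.** Section 3 describes a "Randomized, controlled, crossover study" with three conditions (TF, FR and control, CON), one per session, spaced "Minimum 24 h, maximum 5 days between sessions". The outcome list in section 5 gives three assessments per session: "Baseline, 1 min post, 15 min post intervention". Section 6 names the primary analysis, "Two-way repeated measures ANOVA (Condition × Time", followed by a Bonferroni correction for post hoc tests, and gives the software as "SPSS v25.0; MATLAB for data organization/graphs".

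The protocol also allows for loss. The sample size paragraph in section 4 states a requirement of 21 and adds: "To account for dropout, 30 participants enrolled". Section 7 grants the "Right to withdraw at any time without consequence". The primary objective in section 2 is the comparison of TF with FR.

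**The concern.** Both factors in the ANOVA vary within the player. The classical procedure needs every player's full row of cells and omits the whole player, for that outcome, when one cell is empty. Because the conditions fall on separate days, dropout here will often mean that a player finished some sessions and not others.

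Two cases show the cost. A player who finishes TF and FR and then leaves before CON has supplied everything needed for the primary contrast, yet adds nothing to the fitted model. A player who misses a single 15-minute assessment loses the other eight measurements for that outcome.

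This is how the named method behaves, not a rule left unstated. What is at stake is precision on TF versus FR. There is also possible bias if players fail to return because of how they responded in an earlier session.

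**Working it through.** **Inputs from the protocol.** Required 21 and enrolled 30 (section 4); three conditions in separate sessions (section 3); three assessments per session (section 5); two-way repeated measures ANOVA in SPSS (section 6).

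**The plan's own figure.** The 21 comes with "effect size = 0.398", α = 0.05 and power 0.8, but without the test family, number of measurements, correlation or sphericity correction. Reading 0.398 as Cohen's f, with one group, three measurements and no sphericity correction, the noncentral F calculation gives 22 at correlation 0, 20 at 0.1 and 12 at 0.5. So 21 is neither confirmed nor shown to be wrong, and it is taken as stated below.

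**Margin and cells.** 30 − 21 = 9 players, and 9/30 = 30%. Cells per player per outcome: 3 × 3 = 9.

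**Precision of TF − FR.** Assumptions:
- One change score per session, variance σ², equal correlation ρ between a player's sessions.
- Missed sessions spread evenly over the three conditions.
- Of d incomplete players, d₂ have two sessions, d₁ have one, and the rest have none.

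With n complete players, Var(TF − FR) = 2σ²(1 − ρ)/n. Under generalised least squares on all observed sessions, the information for this contrast equals that of

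n_eq = (30 − d) + (d₂/3)(2 + ρ)/(1 + ρ) + (d₁/3)(1 − ρ)

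complete players. The ANOVA has 30 − d, so its standard error is larger by the factor √[n_eq/(30 − d)].

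Worked case: d = 9, each missing one session, ρ = 0.5. n_eq = 21 + 3 × 2.5/1.5 = 26.0, and √(26.0/21) = 1.113.

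| Pattern, d = 9 | n_eq at ρ = 0 / 0.5 / 0.9 | SE excess |
|---|---|---|
| Each misses exactly one session | 27.0 / 26.0 / 25.6 | 13.4 / 11.3 / 10.4% |
| Half leave after one session, half after two | 25.5 / 24.3 / 23.4 | 10.2 / 7.5 / 5.6% |
| One third each before any, after one, after two | 24.0 / 23.2 / 22.6 | 6.9 / 5.0 / 3.8% |
| All leave after one session | 24.0 / 22.5 / 21.3 | 6.9 / 3.5 / 0.7% |

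With fewer losses, each player missing one session:
- d = 6: 8.0% at ρ = 0 down to 6.2% at ρ = 0.9.
- d = 3: 3.6% down to 2.8%. The three-way mixed pattern with d = 3 gives 1.8% down to 1.0%.

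**Edges outside these assumptions.** If all nine leave before any session, n_eq = 21 and nothing is gained. If all nine miss only CON, all 30 TF-FR pairs exist and the factor is √(30/21) = 1.195.

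**Scattered missing assessments.** If each cell is missing independently with probability p, the share of players dropped for an outcome is 1 − (1 − p)⁹. That is 16.6% at p = 0.02 (30 falls to about 25) and 24.0% at p = 0.03 (30 falls to about 23). Both values of p are assumed; the protocol gives none.

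**The case against.** Several points on the other side are sound.

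- **No dropout rate is stated.** A reader might infer that the protocol expects nine losses. It does not say so; nine is only 30 − 21.
- **The stated requirement survives.** A reader might infer that the trial would be underpowered. Enrolling extra players is the protocol's answer to loss, and with up to nine incomplete the stated 21 remain.
- **Not necessarily every comparison.** Section 6 names a Bonferroni correction but no post hoc procedure. Marginal-mean comparisons from the fitted ANOVA lose the incomplete players; separate paired tests would keep every TF-FR pair. The protocol does not say which is meant, so the loss is certain only for the model and what is derived from it.
- **The size depends on the pattern.** The 10–13% needs all nine spare players to miss exactly one session each. If they leave after one session it is 1–7%.
- **Bias is hypothetical.** Nothing in the protocol suggests response-related withdrawal, and section 7 describes minimal risk.
- **An unseen analysis plan might add rules**, such as imputation. That could soften the effect.

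The last point does not remove the concern, because the protocol itself names the ANOVA as primary while allowing for dropout. The others limit its size and wording but leave the mechanism intact.

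**Conclusion.** The point holds as a matter of efficiency. The named primary method can discard completed TF and FR sessions from the main contrast under the partial dropout that this design allows.

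With nine incomplete players, the TF-FR standard error is about 1–13% larger than an analysis of all observed data would give. With three it is at most about 4% larger, and with complete data the loss is nil. These figures assume equal correlation between sessions, losses spread evenly over conditions, and (for the lower end) at least one completed session per player.

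Complete-case estimates could also be biased if non-return depends on an earlier observed response. A correctly specified likelihood model would remain valid in that case, but the protocol gives no evidence that it will arise.

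The protocol does not support the stronger conclusions that the sample size fails or that the ANOVA is invalid. With complete data it is a legitimate analysis of this design. The change is worth making because it is cheap, not because the trial fails without it.

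**What to change.** In section 6, make the primary analysis a linear mixed model (SPSS MIXED, REML, small-sample degrees of freedom where available), specified as follows:
- Fixed effects: Condition, Time, Condition × Time and Period (session order). Period belongs in the model because withdrawal removes later sessions selectively.
- Random effects: participant and session within participant, or a less restrictive covariance within session.
- Data: all observed measurements from every randomised player, including those who leave after one or two sessions.

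Keep the Bonferroni comparisons and state that they come from this model. Report the complete-case ANOVA, with partial eta squared, as a sensitivity analysis.

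The cost is a short rewording of section 6 and slightly more analysis work, with no new data, visits or software. There are two small downsides: a covariance structure must be chosen in advance, and partial eta squared would come from the complete-case set rather than from the primary analysis set.

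### The post hoc Bonferroni rule is valid but needlessly conservative: Holm controls the same error for the same family and never rejects less

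*Protocol*

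**What the plan says.** Section 3 describes a "Randomized, controlled, crossover study" with three conditions: tissue flossing (TF), foam rolling (FR) and control (CON). Outcomes are taken at "Baseline, 1 min post, 15 min post intervention" (section 5, Outcome Measures).

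Section 6 makes the primary analysis a "Two-way repeated measures ANOVA (Condition × Time" model. It gives the post hoc method as "Bonferroni correction" and sets the threshold at 0.05. It does not say which comparisons the correction covers: the three condition pairs, the time pairs, or both.

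The primary objective in section 2 sets TF against FR. A three-condition ANOVA answers that through a pairwise comparison, so the post hoc rule decides the main question. The sample size paragraph in section 4 gives 21 players as "required (effect size = 0.398", with alpha 0.05 and power 0.8, and then states: "To account for dropout, 30 participants enrolled".

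**The concern.** If the family is the three condition pairs, Bonferroni judges TF versus FR at 0.05/3 = 0.0167, whatever the other two pairs show. Bonferroni spends alpha as though all three pairwise nulls might still be true after one has been rejected. Step-down and closed procedures use the fact that they cannot all be.

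What is at stake is power for TF versus FR in a trial of 30 players. The validity of any positive result is not in question.

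**Working it through.** **1. The plan's own figure.** For one group and m repeated measures, the noncentrality is λ = f²·n·m/(1−ρ). With f = 0.398, m = 3, ρ = 0 and n = 21, λ = 0.1584 × 63 = 9.98. Power is then 78.3%, and n = 22 is needed for 80%. Exactly 21 results from m = 2, ρ = 0.25, or from m = 3, ρ = 0.25 and a sphericity factor of 0.75. Read as a two-sided paired d, 0.398 would need 52. So 21 is reproduced within rounding but not uniquely. The protocol gives no paired TF-FR effect, and the effects below are assumptions.

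**2. Why Holm never loses.** For m tests, Bonferroni rejects when p ≤ α/m. Holm compares the k-th smallest p-value with α/(m−k+1), stopping at the first failure. Each of these limits is at least α/m, so every Bonferroni rejection is also a Holm rejection. If m₀ nulls are true, the first of them to be rejected must meet a limit of at most α/m₀, so the family-wise error is at most m₀ × α/m₀ = α. This holds for any family and any correlation, so the unnamed family does not matter here.

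**3. Bonferroni power and the ceiling on any gain.** Assume the family is three pairs at one time point, two-sided tests, equal SDs of the three pairwise differences, and d in units of that SD. Power comes from the noncentral t with δ = d√n.
- n = 30, d = 0.5: δ = 2.74, 29 df. At 0.0167 (critical t 2.54) power is 58.3%; at 0.05 (critical t 2.05) it is 75.4%.
- n = 21, d = 0.65: δ = 2.98, 20 df. At 0.0167 (critical t 2.61) power is 64.4%; at 0.05 (critical t 2.09) it is 80.9%.

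No procedure that tests each pair at 0.05 or below can gain more than 75.4 − 58.3 = 17.1 or 80.9 − 64.4 = 16.5 points.

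**4. Simulated TF-FR power (%)**, with the closed test gated by a 2-df multivariate test on the same contrast:

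| Setting | Method | CON midway between TF and FR | FR = CON | FR midway between TF and CON |
|---|---|---|---|---|
| n = 30, d = 0.5 | Bonferroni | 58 | 58 | 58 |
| | Holm | 59 | 62 | 73 |
| | Closed test | 62 | 69 | 75 |
| n = 21, d = 0.65 | Bonferroni | 65 | 64 | 64 |
| | Holm | 66 | 68 | 79 |
| | Closed test | 68 | 75 | 81 |

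- Holm: the smallest gain is about 1 point. The largest are 72.6 − 58.4 = 14.2 and 78.7 − 64.4 = 14.3.
- Closed test: the smallest gains are 62.3 − 58.4 = 3.9 and 68.1 − 64.7 = 3.4. The largest are 75.4 − 58.4 = 17.0 and 80.6 − 64.4 = 16.2.

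**5. Other readings of 0.398.** As a paired d, Bonferroni power is about 24% at n = 21 and 37% at n = 30. Holm gives 25 to 32% and 38 to 49%. A closed test with the ordinary 2-df condition F as gate gains 6 to 17 and 6 to 18 points. Read as f, with ρ of 0 or 0.5, the closed test gains between about 0 and 19 points.

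**6. Error control.**
- *Closed test, one contrast.* With three conditions, once equality of all three is false, at most one pairwise null can be true. Each pair may then be tested at 0.05. Simulated family-wise error was 4.5 to 5.1%.
- *Wrong gate.* Suppose the planned 4-df Condition × Time F gates unadjusted pairs, and the effect (1.2 SD) is present at 1 minute only. False positives at 15 minutes are then 10% (n = 21) to 12% (n = 30), against about 4% with Bonferroni over three pairs.
- *Both times together, no effect anywhere.* Error per outcome is 9.2 to 9.3% with a separate 2-df gate at each time, 8.3 to 8.4% with ungated Bonferroni, and 3.5 to 3.6% with Bonferroni after a significant interaction. When every null is true, Holm makes an error exactly when the smallest p-value is at most 0.05/3, as Bonferroni does. It therefore shares the Bonferroni figures.

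**The case against.** The strongest reply is that Bonferroni controls the error it is meant to control, so nothing in section 6 is wrong and another method is a matter of taste. The first half stands. The second does not: Holm needs no further assumption and never rejects less, so it is better by the plan's own criterion.

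Four stronger readings are tempting, and the protocol does not support them.

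- *The plan fixes a family of three pairs at 0.0167 each.* This is the natural reading, but section 6 names no family, and time comparisons could belong to it. The power figures are conditional on it; the superiority of Holm is not.
- *About 9 to 17 points of power are lost.* That range leaves out the case of CON lying between TF and FR, where the closed test gains only 3 to 4 points and Holm about 1. It also needs effect sizes that the protocol does not give.
- *Each pair can be tested at 0.05 once the planned ANOVA is significant.* The planned omnibus test of interest is the interaction, and with that gate the error reaches 10 to 12% at a time point with no effect. The closed test needs its own gate for each contrast. Even then, its error over both times is slightly above that of ungated Bonferroni and well above that of Bonferroni after a significant interaction.
- *The secondary objective is a joint claim that needs no correction.* It reads "To explore whether TF provides superior improvements in force development compared with FR and CON". That is exploratory wording and does not require both comparisons to succeed.

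One practical objection also stands. Parts of the protocol are in the past tense, including the enrolment statement. Relaxing a threshold after outcome data have been seen would draw a fair criticism of its own.

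**Conclusion.** The point holds as a modest, cheap improvement in efficiency. That Holm is at least as powerful as Bonferroni at the same family-wise error is certain for any family. The size is not certain. For three condition pairs at one time point, two-sided tests, equal pairwise SDs and the assumed effects (n = 30, d = 0.5; n = 21, d = 0.65), Holm adds about 1 to 14 points of TF-FR power and a correctly gated closed test about 3 to 17. The top of each range needs FR to lie between TF and CON; the bottom applies when CON lies between TF and FR. A reader should not infer that the plan's inference is invalid: any pair declared significant under Bonferroni would also be declared under Holm.

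**What to change.** In section 6, replace the post hoc entry by: *Holm correction over the three condition pairs (TF-FR, TF-CON, FR-CON) for each outcome and post-intervention time.* Keep the planned Condition × Time ANOVA. This also names the family, which is useful whichever correction is used.

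Optional alternative: for each outcome and post-intervention time, test the three conditions' changes from baseline with a 2-df condition test at 0.05. Only if it is significant, test each pair at 0.05; otherwise declare none. State that the 4-df interaction F does not serve as the gate for unadjusted pairs.

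The cost is one sentence. Holm needs only the three unadjusted p-values and no extra players or data. There are two downsides. Stepwise tests have no simple matching simultaneous confidence intervals, so ordinary 95% intervals would be reported and labelled as such. Error control is per outcome and time point only, and the text should say so. The change should be made, and dated, before any outcome data are examined by condition.
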